## **4 STATISTICAL ANALYSES**

All statistical analyses will be performed using the SAS® software (Version 9.4 or later). It will be based on data according to CDISC standards, SDTM (SDTM IG v3.3) and ADaM (ADaM IG v1.3).

Descriptive statistics will be given by treatment group and overall, where appropriate.

Statistical Analysis Plan	Version 1.0		Page 12 of 37
Sponsor	SOM Biotech	Protocol No	SOMCT03

If not stated otherwise, the following standard types of descriptive analyses will be presented:

## Descriptive statistics for continuous data

N, mean, SD, min, median and max will be presented. These descriptive statistics will be determined for measured values and for changes from baseline.

## - Descriptive statistics for categorical data

Absolute frequencies and percentages will be presented. Percentage bases (denominators) will be identified in the table title or footnote (i.e. all patients at risk, all nonmissing cases, all cases). For changes from baseline, shift tables may be generated.

## Inferential statistics

Unless otherwise stated, all statistical tests will be performed two-sided and at a type I error probability of  $\alpha$ =0.05. The p-values will be printed consistently with 4 decimals (p<0.0001 will be displayed, if the p-values are less than 0.0001 and p>0.9999 will be displayed, if the p-values is more than 0.9999).

Unless otherwise stated, all confidence intervals (CIs) will be derived two-sided and at a confidence probability of  $1-\alpha=0.95$ .

## Listings

All recorded data will be listed by patient (sorted by treatment group Placebo, 200 mg BID, 300 mg BID). Identification variables are centre number, patient number and treatment group.

Derived data will be stored in special analysis data sets and will be calculated as outlined in section 6.1.

#### 4.1 Conventions

#### 4.1.1 Baseline definition

Baseline is defined according to the endpoint as follows:

- For the Total Maximal Chorea score (TMC), and motor part of Unified Huntington's Disease Rating Scale (UHDRS-TMS) the baseline is defined as the average of the values for Visit 0 and Visit 1.
- The severity of choreic symptoms is assessed at Visit 1 with Clinical Global Impression-severity (CGI-S) scale and Patient Global Impression-severity (PGI-S) scales. Score of these 2 scales is assessed at baseline but cannot be used as baseline value when calculating changes to baseline, since change is already assessed at each visit (Visit 2 to Visit 6) with Clinical Global Impression of Change (CGI-C) and Patient Global Impression of Change (PGI-C).
- For EQ-5D, Barnes Akathisia Rating Scale (BARS), Montreal Cognitive Assessment (MoCA) scale and Problem Behavior Assessment short form (PBA-s) baseline is the value at Visit 1.

Statistical Analysis Plan	Version 1.0		Page 13 of 37
Sponsor	SOM Biotech	Protocol No	SOMCT03

- For the Total Functional Capacity score (TFC), Columbia Suicide Severity Rating Scale (C-SSRS), Beck Depression Inventory (BDI), Epworth Sleepiness Scale (ESS), ECG and vital signs, baseline is defined as the value at Visit 1.
- For Functional Assessment (FA) of the UHDRS baseline is at Visit 0.
- For laboratory data (haematology and clinical chemistry), baseline is at Visit 0.
- For any other parameter, baseline is defined as the last available measurement before the first administration of study drug, i.e., the value of the parameter at Visit 0 or at Visit 1.

## 4.1.2 Missing data

In case of premature discontinuation, values collected at the end of study visit (EOS) or Unscheduled Visit (if it is the last visit) will be imputed to the first missing visit of the patients. For example, a patient withdrew between V3 and V4 (i.e. V4 is missing), then the value recorded at EOS will be imputed to V4. If a patient discontinues exactly at the time of a visit, but the value is recorded in the EOS page, this value will be imputed to the visit when the discontinuation occurred.

Partial dates are allowed on the eCRF for adverse event (AE) onset and resolution dates, concomitant medication start and stop dates, and concomitant procedure dates. An entry for the year is required in the eCRF system for each of these dates. Only the month and day may be entered as unknown. Dates from these forms will be reported in listings as collected. Every effort will be made to query missing dates particularly to clarify the onset day and time of AE occurring at visit 1 to determine if the AE is treatment emergent or not.

For records with missing AE onset date, the following procedure will be employed for use in determining whether the AE is treatment emergent:

- AE onset dates with missing day and non-missing month will be assumed to occur on the first day of the non-missing month, except for AEs occurring in the first month of dosing, in which case the date will be set to the first day of dosing.
- AE onset dates with missing month will be assumed to occur on the first day of the non-missing year (i.e., January 1), except for AEs occurring in the first year of dosing, in which case the date will be the first day of dosing.

For records with a missing medication start and/or stop date, the following procedure will be employed for use in determining whether the medication is prior or concomitant:

- Medication start dates with a missing day and non-missing month will be assumed
  to occur on the first day of the non-missing month, except for medications occurring in the first month of dosing, in which case the date will be the first day of
  dosing.
- Medication start dates with missing month will be assumed to occur on the first day of the non-missing year (i.e., January 1), except for medications occurring in the first year of dosing, in which case the date will be the first day of dosing.

Statistical Analysis Plan	Version 1.0		Page 14 of 37
Sponsor	SOM Biotech	Protocol No	SOMCT03

- Medications that are not ongoing and have a medication stop date with a missing
  day and non-missing month will be assumed to occur on the last day of the nonmissing month.
- Medications that are not ongoing and have a medication stop date with a missing month will be assumed to occur on the last day of the non-missing year (i.e., December 31).

For records with a missing procedure date, the following procedure will be employed for use in determining whether the procedure is prior or concomitant:

- Procedure dates with a missing day and non-missing month will be assumed to
  occur on the first day of the non-missing month, except for procedures occurring
  in the first month of dosing, in which case the date will be the first day of dosing.
- Procedure dates with missing month will be assumed to occur on the first day of the non-missing year (i.e., January 1), except for procedures occurring in the first year of dosing, in which case the date will be the first day of dosing.

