## 2.2 Deviations from the trial protocol with regard to statistical analyses

The following deviations from the protocol were identified as being important for the statistical analysis:

For the key secondary efficacy endpoint (Change from baseline in the Clinical Global Impression (CGI-C)) multiplicity adjustment will be applied.

Original text in protocol: The type I error will be set at 0.05 (two-sided) and the coverage level of confidence intervals to 95% for all secondary efficacy analyses. No multiplicity adjustment will be applied for the statistical inferences of the secondary efficacy endpoints.

Statistical Analysis Plan	Version 1.0		Page 9 of 37
Sponsor	SOM Biotech	Protocol No	SOMCT03

The revised definition in SAP only for key secondary endpoint: To preserve the family-wise error rate at the 0.05 level when comparing the two doses of SOM3355 versus placebo and comparing a primary endpoint and key secondary endpoint, statistical testing will be carried out using the Holm procedure for CGI-C if the primary endpoint is significant for both doses. The smallest p-value of the two comparisons will be first compared at the two-sided 0.025 level and if statistically significant, the other p-value will be compared at the two-sided 0.05 level.

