## 4.4 IMP exposure and compliance

## **Exposure:**

- Total number of patients with at least one dose of study treatment: overall and per treatment periods (W1 (200mg once daily (OD) or Placebo), W2 (200mg BID or Placebo), W3 (200 or 300mg BID or Placebo), W4-W10 (200 or 300mg BID or Placebo), W11 (200mg OD or Placebo), W12 (Placebo))
- Total number of days with at least one dose of study treatment: overall and per treatment periods (W1 (200mg OD or Placebo), W2(200mg BID or Placebo), W3, W4-W10 (200 or 300mg BID or Placebo), W11(200mg OD or Placebo), W12 (Placebo)).

The earliest date of study withdrawal/completion or product withdrawn (AE) will be selected and the day before this date will be defined as the last treatment intake. The first date of administration is collected by visit in the eCRF. Within visits, the intake of study treatment will be defined according to the study protocol and is theoretical.

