## 4.7.1 Primary endpoint

The primary endpoint is the change in Total Maximal Chorea (TMC) score from baseline (defined for each patient as the average of values at the screening visit (Visit 0) and the inclusion visit (Visit 1)) to the end of maintenance therapy (defined for each patient as the average of values at the end of Week 9 (Visit 4) and the end of Week 10 (Visit 5)).

As a result, the different factors included in the MMRM model (below) will be defined as following:

- Baseline TMC: calculated as (TMC V0 + TMC V1)/2,
- TMC at each following Visits: V2 (week 3), V3 (week 6), V4 (week 9), V5 (week 10)),
- Change from baseline TMC: [(TMC V4 + TMC V5)/2 Baseline TMC]

If the value at V5 is missing and V4 is not missing, then the value at V4 will be used for the calculation. If the value at V4 is missing and V5 is not missing, then the value at V5 will be used for the calculation. If both V4 and V5 values are missing, change from baseline TMC will be treated as missing.

The estimand of the primary efficacy analysis is defined according to ICH-E9-R1. The estimand reflects a mixed strategy for the inter-current events as presented in the table below.

Estimand attribute	Primary definition	Rationale (as needed)
Population	Patients with Huntington's disease with choreic movements	

Statistical Analysis Plan	Version 1.0		Page 18 of 37
Sponsor	SOM Biotech	Protocol No	SOMCT03

Estimand attribute	Primary definition		Rationale (as needed)
Endpoint	Change from baseline (Visit 0 and Visit 1) to end of maintenance dose (Visit 4 and Visit 5) in TMC score		
	Event	Strategy	Rationale (as needed)
	Receipt of assigned study treatment	Treatment policy	This strategy applied to align the estimand with the application of the ITT principle.
Inter-current events	Prohibited concomitant neuroleptic treatment during the treatment period	While on treat- men	This strategy applied up to the time of the prohibited concomitant treatment.
	Discontinuation from study	Hypothetical policy	This strategy applied for randomized and treated patients using a MMRM approach under MAR assumptions.
Summary measure	Difference in the change of TMC score from baseline to end of maintenance visit adjusted LS means between active arms and placebo		

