The primary analysis of the primary efficacy endpoint will be based on a mixed-effect linear model for repeated measures (MMRM) to compare each active treatment group to placebo. The model will include the following factors: treatment group, visit, and treatment-by-visit interaction as fixed effects, and baseline TMC score as covariate. An unstructured (UN) variance-covariance matrix will be used to model the within-patient errors. If no reliable results under the UN assumption can be obtained, the Toeplitz (TP) covariance structure, followed by the autoregressive (AR1) and Compound Symmetry (CS) covariance structure will be used. The Kenward-Roger method will be used to estimate the denominator degree of freedom.

The SAS code for the primary analysis is as follows:

PROC MIXED data=dataset method=REML;

CLASS subject treatment visit;

MODEL changeTMC = treatment visit treatment\*visit baselineTMC / ddfm=KR;

REPEATED visit / subject = subject type = UN;

LSMESTIMATE treatment\*visit "TMC change 200 mg vs Placebo" 0 0 -1 0 0 1 0 0 0 / cl elsm;

LSMESTIMATE treatment\*visit "TMC change 300 mg vs Placebo" 0 0 -1 0 0 0 0 0 1/cl elsm:

RUN;

Statistical Analysis Plan	Version 1.0		Page 19 of 37
Sponsor	SOM Biotech	Protocol No	SOMCT03

The least squares mean (LSM) estimate for each treatment group and difference in LSM estimates at end of maintenance dose between active treatments and placebo group with their confidence intervals will be provided. For the lowest p-value 97.5% CI will be provided and for the highest p-value 95% CI will be provided.

To preserve the family-wise error rate at the 0.05 level when comparing the two doses of SOM3355 versus placebo, statistical testing will be carried out using the Holm procedure. The smallest p-value of the two comparisons will be first compared at the two-sided 0.025 level and if statistically significant, the other p-value will be compared at the two-sided 0.05 level.

Descriptive statistics will be presented for the TMC score and changes from baseline by treatment group and by visit (including V6), on imputed data (as described in 4.1.). In addition, time profiles of the mean TMC scores with standard error of the mean (SEM) will be presented.

Sensitivity analyses on the primary efficacy endpoint will be conducted as follows:

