## Sensitivity #1

A sensitivity analysis will be performed to assess the robustness of the primary analysis based on MMRM. Intermittent missing values will first be imputed using the Markov Chain Monte Carlo (MCMC) method which assumes a joint multivariate normal model for variables in the imputation model. Then a control-based pattern imputation is applied to the monotone missing data under the assumption of data missing not at random (MNAR). PROC MI using the MCMC statement will be used to implement the first step. Then PROC MI using the MONOTONE and MNAR statements will be used to create the complete data sets. MNAR will be imputed using Copy Reference method and number of imputations will be 30. The same MMRM analysis as defined for the primary analysis will be performed on the complete data sets, and the results will be combined using PROC MIANALYZE. This analysis will be performed on the mITT population.

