## Sensitivity #4

The primary efficacy analysis will be repeated using data without imputation for the visits of discontinued patients for the mITT population.

Subgroup analysis as defined in section 3.6 will be performed for the primary endpoint across all predefined groups, with a particular focus on comparing patients taking neuroleptics as concomitant medication during the study versus patients not taking neuroleptics during the study. For this subgroup, descriptive statistics for the TMC score and changes

Statistical Analysis Plan	Version 1.0		Page 20 of 37
Sponsor	SOM Biotech	Protocol No	SOMCT03

from baseline by treatment group and by visit (including V6) will be presented, as well as time profiles of the mean TMC scores with standard error of the mean (SEM) will be provided.

For the subgroup analysis assessing patients with correct versus incorrect down titration phase between V5 and V6, only descriptive statistics for TMC score on visits will be repeated on the mITT to show the evolution of the TMC score between V5 and V6 after IMP interruption.

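### The SAP fills a withdrawn patient's next visit with the end-of-study TMC value, although the estimand handles withdrawal by MMRM under MAR

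*SAP*

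**What the plan says.** **Estimand.** Protocol 9.4.1 (Table 4) and SAP 4.7.1 both assign discontinuation from the study to a hypothetical strategy, with the rationale "This strategy applied for randomized and treated patients using a MMRM approach under MAR assumptions".

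**Missing-data rule.** For patients who stop early, SAP 4.1.2 states: "values collected at the end of study visit (EOS) or Unscheduled Visit (if it is the last visit) will be imputed". The reading goes into the earliest visit the patient lacks. The SAP's own example is withdrawal between Visits 3 and 4, where the end-of-study (EOS) value becomes Visit 4. A further sentence covers patients who stop exactly at a visit.

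**Endpoint rule.** The endpoint is the mean of Visits 4 and 5 minus baseline. SAP 4.7.1 adds: "If the value at V5 is missing and V4 is not missing, then the value at V4 will be used for the calculation".

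**Where the fill applies.** Descriptive TMC statistics are given "by visit (including V6), on imputed data (as described in 4.1".) Sensitivity #4 reads: "The primary efficacy analysis will be repeated using data without imputation for the visits of discontinued patients", on the mITT population.

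**Declared changes.** SAP 2.2 opens with "The following deviations from the protocol were identified as being important for the statistical analysis" and then lists only the multiplicity adjustment for CGI-C.

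**The concern.** Under the stated strategy, scheduled visits after withdrawal stay missing and the model handles them from the data observed earlier. The 4.1.2 rule instead takes a reading made at one time and labels it as a later visit. No limit is set on how far the reading may be from that visit, or on how long the patient has been off drug.

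If the reading is off drug, the active-placebo difference is pulled toward zero, and more in an arm that loses more patients. The protocol (4.3) intends the study to identify the dose for Phase 3, so uneven dilution between doses matters. SAP 4.12 says the futility analysis uses the same method and code as the primary endpoint. Dilution is conservative for a superiority test, but it makes a futility stop more likely.

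Sensitivity #1 has a related gap. There, "a control-based pattern imputation is applied to the monotone missing data", but the SAP does not say whether the starting data are already filled. If they are, a patient who withdrew between Visits 3 and 4 has no missing endpoint left for copy-reference to test.

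**Working it through.** **1. Does the fill reach the primary analysis?** No single sentence says so. Sensitivity #4 repeats the primary analysis without the fill, and would duplicate it if the primary were unfilled. The model contrasts have nine coefficients (three arms by three visit levels), which fits Visit 2, Visit 3 and a combined Visit 4/5. The fill therefore enters the endpoint.

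**2. The plan's own figure.** Inputs from protocol 9.3 and SAP 1.4: difference 2.5, SD 3.5, two-sided 0.025, t-test. The noncentral t gives 39 per arm with 80.5% power, as stated. With 43 randomized and 10% lost, 43 × 0.9 = 38.7 remain.

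**3. Who is affected.** The documents give no dropout timing. Assume dropout D is spread evenly over 10 weeks. Visits 3, 4 and 5 are at Weeks 6, 9 and 10, so 0.3D withdraws between Visits 3 and 4 and 0.1D between Visits 4 and 5. For D = 0.10 that is 3% + 1% = 4% of an arm, or 0.04 × 43 = 1.7 patients.

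**4. Direct effect.** Let r be the share of drug effect still present at the EOS reading (not given; range 0 to 1). A Visit 4-5 withdrawal has half weight, because the filled value is averaged with an observed Visit 4.

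- Filled: share contributing = 1 − D + 0.3D + 0.1D; difference = 2.5 × [1 − (0.3D + 0.05D)(1 − r)/share].
- Unfilled: share = 1 − D + 0.1D; difference = 2.5.

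For D = 0.10, the filled share is 0.94 (40.4 per arm) and the unfilled share is 0.91 (39.1 per arm). With r = 0: 2.5 × (1 − 0.035/0.94) = 2.41.

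| Analysis | Difference | Power per comparison |
|---|---|---|
| Filled, r = 0 | -2.41 | 78.8% |
| Filled, r = 0.5 | -2.45 | 80.5% |
| Filled, r = 1 | -2.50 | 82.1% |
| Unfilled | -2.50 | 80.7% |

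**5. Upper scenarios (r = 0, direct effect only).**

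- All of the 10% dropout between Visits 3 and 4: 2.5 × 0.9 = 2.25, power 75.6%, against 80.2% unfilled.
- Dropout 15% on active and 5% on placebo: the active share is 0.91 and the shift is 2.5 × 0.0525/0.91 = 0.14, giving -2.36 and 76.9%, against 80.6% unfilled. An active arm with 5% dropout would shift by 2.5 × 0.0175/0.97 = 0.05.

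**6. Indirect path.** Earlier withdrawals have Visit 2 or 3 filled, and these values act on the endpoint through the covariance. This was simulated with 8,000 two-arm trials per setting, an assumed within-patient correlation of 0.5 or 0.7, and an assumed effect of 2.5 at every visit. At D = 0.10:

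- r = 0: -2.34 to -2.32, power 77%, against about 82% unfilled.
- r = 0.5: -2.42 to -2.41, power 80%, against 82% unfilled.
- r = 1: -2.50.

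**The case against.** The EOS value is a real observation, not a modelled one, and only the first missing visit is filled; later visits stay missing. Few patients are affected. Nothing in the documents shows that effect is lost by the EOS visit. The SAP 4.4 rule that "the day before this date will be defined as the last treatment intake" is an exposure-counting convention, and patients also attend Visits 2 to 5 before their morning dose. In the even-dropout case, filled and unfilled power are equal when about 55% of the effect remains; above that, filling gains power. With half the effect kept, even the case with all dropout between Visits 3 and 4 gives 80.4% filled against 80.2% unfilled. Sensitivity #4 is already planned, so both results will be seen.

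Most of this stands as a limit on size. The total-loss figures are upper bounds, and a one-day gap alone does not make the EOS reading differ from a scheduled pre-dose reading. The effect on the futility rule is not quantified, and that rule is non-binding. None of it removes the mismatch. A value observed at its own scheduled visit belongs in the analysis, on or off drug; the fault is in moving a value to a later visit with no time limit. Having the matching analysis as a sensitivity analysis also leaves the headline result on a different footing from the named estimand. Whether the rule counts as an important deviation from the protocol can be argued, but it alters primary endpoint values and the protocol's primary analysis contains no such rule.

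**Conclusion.** The concern holds as an inconsistency between the estimand and its primary analysis, and should be fixed. With 10% dropout spread evenly, the direct bias is 0 to 0.09 points on a planned 2.5. Power changes by between +1.4 and -1.8 percentage points relative to the unfilled analysis. Including the indirect path, total effect loss brings the bias to about 0.16 to 0.18 points; the largest shift among the scenarios examined is 0.25. All of these rest on assumed dropout timing and retained effect, and the indirect figures also on assumed correlations. In these scenarios the shift is toward no effect, so type I error inflation is not the worry. The worry is a headline estimate that is not the one named, and that may be diluted unequally across doses.

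A separate point, on which this conclusion does not rest: the protocol's intercurrent event is any prohibited concomitant treatment, while the SAP's is prohibited neuroleptics only. SAP 2.2 does not declare the narrowing, and no analysis step applies the while-on-treatment strategy to either version.

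**What to change.** Before database lock:

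1. Make Sensitivity #4 (the MMRM without EOS or unscheduled filling) the primary analysis, and move the filled version to sensitivity.
2. Map an EOS-page or unscheduled value to a scheduled visit only if it was taken at that visit, within the protocol's ±2-day window, on or off drug. This keeps the 4.1.2 sentence on patients who stop exactly at a visit.
3. State that Sensitivity #1 starts from unfilled data.
4. Record the change in SAP 2.2.
5. Separately, restore the protocol's wording for prohibited treatment, or declare and justify the narrowing. Give the data rule for TMC values after that event. Setting them to missing under MAR is a hypothetical strategy; if while-on-treatment is kept, define which pre-event value is used.

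The cost is SAP wording and a swap of two planned analyses. About 1.3 fewer patients per arm contribute an endpoint value (39.1 instead of 40.4 of 43). Any patient whose only post-baseline TMC falls outside every visit window would meet the mITT definition but add nothing to the model; report how many there are.
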